3.1.3 Key behavioral and biological indicators

Behavioral Indicators

- Sexual risk behavior including number and type of sex partners ("commercial", "regular" and "non-regular")
- Condom use with different types of sex partners
- Other practices related to condom use and safe sex
- Knowledge of STIs and STI care-seeking behaviors
- Knowledge and attitudes toward HIV/AIDS
- Drug and substance use (including injecting and equipment sharing)
- Mobility and migration patterns influencing sexual behavior and risk
- Perception of HIV and STI risk
- Exposure to Avahan and other HIV/AIDS prevention interventions

Biological Indicators

- STI prevalence (syphilis serology, *N. gonorrhoeae* (Ng), *C. trachomatis* (Ct), herpes simplex virus (HSV) 2 serology, HBC and HCV in IDUs, and for those reporting ulcers *T. pallidum* (Tp), *H. ducreyi* (Hd) and HSV-2 antigen detection)
- HIV prevalence
- HIV incidence (BED-CEIA validated for Indian sub-type C)

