4.2 IBBA Procedures

4.2.1 *The behavioral assessment*

For the behavioral assessment, standardized behavioral questionnaires for the different sub-groups included in the IBBA will be used. Care will be taken to ensure that the data needed for impact modeling are also gathered in the IBBA. The information that will be obtained using the behavioral questionnaire will include:

- Socio-demographic characteristics;
- Sexual history and practices (penile-vaginal, oral, anal);
- Types of sex partners;
- Condom use with different type of sex partners;
- Knowledge of STIs and STI care-seeking behaviors;
- Knowledge and attitudes toward HIV/AIDS;
- Sex purchasing and selling behaviors among males with other males;
- Needle, syringe and drug sharing practices among IDU (and other groups who may inject such as FSWs);
- Questions related to mobility; and
- Exposure to Avahan and other HIV/AIDS prevention interventions

The questionnaires will be adapted to local needs (language, terminology) and will be pre-tested in all IBBA areas. Before pre-testing, the questionnaires will be checked for appropriate sequencing and skip patterns and translated to the local language(s) of each state, and back translated to check the accuracy of the translation. Pre-testing the questionnaires will include checking to make sure that the questions are interpretable in a commonly understood manner and that the original meaning of the questions have been kept intact in the process of adapting them. An instruction manual will be developed for interviewers and supervisors which will go through the questionnaire, one question at a time, explaining in full, the rationale behind each question and its intended meaning

4.2.2 *Clinical Procedures*

IBBA procedures for STI testing and treatment and HIV testing and counseling are outlined in the table below.

Venous blood draw on FSW, MSW, MSM, Clients of FSW
 
 • HIV (prevalence/incidence) • Syphilis (RPR_≥ 1:8, TPHA) • HSV2 on subset 
Dry blood spot IDUs
 
 • HIV (prevalence/incidence), HBV, HCV, syphilis (Treponostika)

First catch 20 ml urine - prepare and store for Ng/Ct testing using nucleic acid amplification tests (NAATs)
Self administered vaginal swab – prepare and store for Ng/Ct using NAAT
Ulcer swab 
 • mPCR for TP/HD/HSV2 if report external clinical ulcer

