4.2.2.1 Rationale for STI/HIV testing

As part of the IBBA participants will be tested for STIs and HIV. Following consent procedures (see details below), a venous blood sample and a urine specimen or self-administered vaginal swab will be collected. For IDUs a dry blood spot will be obtained in the place of venous blood. All testing will be linked anonymous testing whereby all specimens are linked only to a unique respondent number.

Participants will be given this number and told that they need to keep the number in order to obtain their syphilis test results, if they so desire. This number system will be supplemented with a personal password/codeword system in the case that the number is lost.

After completion of the behavioral questionnaire and collection of specimens, sex workers (both male and female) will be provided with syndromic STI treatment in a manner consistent with the Avahan program. Ulcers swabs will be taken from all who both report ulcer symptoms and are found upon external examination to have a genital ulcer. Treatment will be given and ulcer swabs transported with the urine and blood samples. More complex cases (e.g. internal ulcers or other symptoms), if they agree, will be accompanied to NGO clinics for more comprehensive evaluation and treatment. Results of syphilis serologic testing will be available at the NGO clinics at a specified time after recruitment. Since results will be labeled with the identification number only; participants will need to present with their numbered card to obtain syphilis results. NGO outreach and peer educators will enforce the importance of returning for syphilis results and treatment in the case of a positive result. All participants will know through the consent process that their blood is being drawn for syphilis and HIV testing and that it will be stored for potential future research on HIV infection.

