The monitoring will be done by the NGO staff accompanying the participants (for those participants who want to be accompanied) and periodic assessment visits by ICMR and FHI.

Details of specimen collection and clinical procedures

The clinical procedures involved in STI prevalence studies are standard medical procedures for clinical examination and clinical specimen collection. All personnel involved in clinical procedures will be medical personnel.

- Collection of 20 ml of first-catch urine, at least two hours since last void, or self-administered vaginal swab for nucleic acid amplification testing for *N. gonorrhoeae* and *C. trachomatis*.
 - Collection of up to ten milliliters (generally 7ml in a vacutainer) of venous blood to test for HIV and syphilis serology. A subset will have stored serum tested for HIV incidence (BED-CEIA), and HSV2. Remaining sera will be stored in the short term for quality control testing and for those participants who consented for long term storage.
-
- For patients reporting GUD symptoms, an external examination will be performed including inspection of genital and anal areas and local lymph nodes looking for local changes: erythema, warts, abrasions, ulcers, swelling and discharge. All genital and anal ulcers identified will be sampled with a Dacron swab for *T pallidum*, HSV-2 and *H ducreyi* using multiplex PCR.

At the conclusion of the IBBA activities, the participants will receive group education on STIs and HIV, be provided with IEC material and information about NGOs/CBOs in the district, condom outlet points and other service providers such as health care providers, and legal aid.

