4.3 Laboratory Procedures

Blood, swabs and urine specimens will be picked up by the laboratory technicians for laboratory tests.

- HIV: Screening for HIV will be done using enzyme-linked immunosorbent assay (ELISA). A positive HIV screening test will be confirmed with a second ELISA and then undergo the BED-CEIA test (see below).
- Syphilis serologic testing performed on sera using a quantitative rapid plasma regain (RPR) screening test with a qualitative Treponema Pallidum Hemagglutination Assay (TPHA) confirmation test.
- Polymerase chain reaction (PCR) for *N. gonorrhoeae*, *C. trachomatis*. First catch of 20 ml urine will be stored in a cool box until they are transported for processing to

laboratories with capabilities to perform PCR tests.

- Multiplex Swab on reported and clinically identified genital or anal ulcers. Dacron swab stored dry at -70°C. Subject batched specimens to multiplex testing for *T pallidum*, *H ducreyi* and Herpes simplex Type 2.
- HSV-2 serology.
- HIV incidence testing: The newly developed BED-CEIA (HIV-1 subtypes B, E, and D, IgG-Capture Enzyme ImmunoAssay) that has also been validated with the Indian sub-type C assay will be used for measuring incidence of HIV.

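### In MSM/MSW the only gonorrhoea and chlamydia specimen is urine, so the unrestricted 'STI prevalence' for Ng/Ct is a urethral figure and only a lower bound on overall prevalence in this group

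*Protocol*

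**What the plan says.** **Specimens.** Every place in the protocol that deals with Ng/Ct specimens names urine, with a vaginal swab as the only alternative.

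- Section 4.2.2 (table of procedures): "First catch 20 ml urine - prepare and store for Ng/Ct testing using nucleic acid amplification tests (NAATs". The next row is the self-administered vaginal swab. Neither row has a separate entry for MSM/MSW.
- Section 4.2.2.1 (rationale): "a venous blood sample and a urine specimen or self-administered vaginal swab will be collected".
- Section 4.2.2.1 (details of specimen collection): "Collection of 20 ml of first-catch urine, at least two hours since last void, or self-administered vaginal swab for nucleic acid amplification testing".
- Section 4.2.4 describes the handling of urine samples.
- Section 4.3 (PCR for Ng and Ct): "First catch of 20 ml urine will be stored in a cool box".

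**Anal sampling.** The one anal specimen is an ulcer swab from participants who report ulcer symptoms: "All genital and anal ulcers identified will be sampled with a Dacron swab". Sections 4.2.2.1 and 4.3 send it to multiplex PCR for *T. pallidum*, HSV-2 and *H. ducreyi*, not for Ng or Ct.

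**Indicator and use.** The biological indicator in section 3.1.3 opens "STI prevalence (syphilis serology" and goes on to Ng and Ct with no anatomical limit. Section 10.1 lists STI prevalence data as an output and treats the outputs together as essential input to the models of infections averted.

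**Population and exposure.** Section 3.1.1 defines male sex workers as men who sold sex to other males and MSM as men who bought or sold sex. It lets these definitions vary by state or district and has hijras sampled separately. The questionnaire content in section 4.2.1 includes "Sexual history and practices (penile-vaginal, oral, anal".

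**The concern.** The name of the indicator is wider than what is measured. Urine from a man shows infection of the urethra. A man infected only at the rectum or throat is recorded as negative. The protocol recognises these exposures, since it enrols men for sex with males and asks about oral and anal practices, but nothing links those answers to the Ng/Ct estimate.

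Two things are at stake. First, the level: a reader or modeller who takes the figure as Ng/Ct prevalence in MSM/MSW will use a number that errs in one direction. Second, comparison: the share of infections that urine can find depends on how the men sampled are exposed. Where the MSM definition differs between states, part of a difference in urine prevalence may come from exposure mix and not from infection.

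**Working it through.** **1. The plan's own figure for this group.** The protocol gives no expected Ng/Ct prevalence. Its only figure for MSM/MSW is the sample size in section 3.3.1, for consistent condom use moving from 50% to 65%, with alpha 0.05, power 90% and design effect 1.5:

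n = [1.96·√(2·0.575·0.425) + 1.2816·√(0.5·0.5 + 0.65·0.35)]² / 0.15² = 226.2, and 226.2 × 1.5 = 339.2.

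The protocol states 339, rounded to 400, so it reproduces with a two-sided alpha. It rests on a behavioural indicator and is not touched by the specimen question.

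**2. Direction of the error.** Let A be the proportion infected at any site, U the proportion with urethral infection (alone or with another site), and E the proportion infected only at rectum or throat. Then A = U + E. Urine estimates U. Since E cannot be negative, U ≤ A, with equality only if no man is infected solely outside the urethra. Sampling error and false positives aside, urine prevalence is a lower bound on overall prevalence. That male urine reflects the urethra is anatomy, not a statement in the documents.

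**3. How large the gap could be (assumptions only).** The documents give neither site-specific prevalence nor the distribution of sexual role. For illustration, suppose that each man is either insertive only (urethral prevalence u) or receptive only (rectal prevalence r), that a share s is receptive, that throat infection is ignored and that the test is perfect. Then urine prevalence = (1 − s)·u and any-site prevalence = (1 − s)·u + s·r.

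| u | r | s | Urine | Any site | Share found |
|---|---|---|---|---|---|
| 5% | 10% | 20% | 4.0% | 6.0% | 67% |
| 5% | 10% | 50% | 2.5% | 7.5% | 33% |
| 5% | 10% | 80% | 1.0% | 9.0% | 11% |
| 5% | 5% | 20% | 4.0% | 5.0% | 80% |
| 5% | 5% | 50% | 2.5% | 5.0% | 50% |
| 5% | 5% | 80% | 1.0% | 5.0% | 20% |

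For the first row: 0.8 × 5% = 4.0%; 4.0% + 0.2 × 10% = 6.0%; 4.0/6.0 = 67%.

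In the last three rows true prevalence is constant at 5%, yet urine prevalence varies fourfold with the mix alone. In the first three, urine prevalence falls while any-site prevalence rises. These rows show the mechanism; they are not estimates for this survey.

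**4. What is not affected.** HIV and syphilis, and HSV-2 on a subset, are tested on blood, so they do not depend on the anatomical site of exposure.

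**The case against.** The strongest reply is that this is a matter of wording. Section 3.1.3 is a one-line list that nowhere claims any-site prevalence, the specimens are openly stated, and urine is a practical field specimen. Labels and caveats can be left to an analysis plan or report. It is true that there is no internal contradiction and that urine is a defensible choice. But the specimen list and the indicator are both fixed in the protocol, and together they determine what the survey can conclude for this group. An output passed on as STI prevalence does not carry the restriction with it.

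Several stronger readings are tempting, and the documents do not support them.

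- *The bias is of a known size.* A reader might assume a true prevalence of 10% with 30% to 70% of infected men positive at the urethra, obtain 3% against 7%, and compute a 56% chance of a falsely significant difference at 400 per sample, or 96% at 1,200 (design effect 1.5). The arithmetic is right, but it sets the two ends of an assumed range against each other. A milder contrast, 4% against 6%, gives 18% and 45%. Nor does the protocol specify a test of Ng/Ct differences in MSM.
- *Sellers are mostly receptive and buyers insertive.* The documents do not say so. They support only that the definitions differ between places and that exposure mix may differ with them.
- *Trends are uninterpretable.* Section 3.1.1 varies definitions by place, not by round. With a stable definition and role mix, the within-district trend in urethral infection can still be read.
- *Programme effect in this group would go unseen.* Condom use by partner type is measured directly and the serological markers are unaffected. One marker in one population group is limited.
- *The impact models are wrong.* Section 10.1 says that the outputs collectively feed the models. It does not say whether, or how, Ng/Ct in MSM enters them.

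The objection also stands on one point of remedy. Section 4.2.1 lists anal practices but does not say that insertive or receptive role is recorded, so reporting by role cannot be taken for granted.

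**Conclusion.** The point holds in a limited form. As written, the plan measures urethral Ng/Ct in MSM/MSW (and hijras where sampled) and names it without that limit. The figure is a lower bound on overall Ng/Ct prevalence in this group, and comparisons between states with different MSM definitions may partly reflect exposure mix.

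The direction follows from the specimen list and anatomy. The size is unknown from the documents: the shares found in the table, 11% to 80%, come entirely from assumed values of u, r and s. The change is worth making because it narrows a claim that the data cannot support, at almost no cost.

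**What to change.** 1. In sections 3.1.3 and 10.1, define the indicator for MSM, MSW and hijras as *urethral Ng/Ct prevalence (urine NAAT)*, and state that it does not estimate overall Ng/Ct prevalence.
2. Give it to the modelling partner with that restriction and a sensitivity range for the untested sites. If φ is the share of infected men who are positive at the urethra, overall prevalence is U/φ. An assumed φ of 0.7 to 0.3 multiplies the urine figure by 1/0.7 = 1.4 up to 1/0.3 = 3.3. The range must be labelled as an assumption.
3. Confirm whether the questionnaire records insertive and receptive practice. If it does, show the indicator by reported practice in a descriptive table at pooled state or project level. District tables would be too sparse: the illustrative 1.0% to 4.0% of 400 men is 4 to 16 positives before any split. Such a table describes the exposure mix; it does not recover missed infections.

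The cost is a change of wording, a note to the modelling partner and, if role is recorded, one extra table. No new specimen is required. The downside is a narrower headline claim for this group.

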4.2.2.2 Consent procedures

A detailed and standardized consent process will be conducted for each respondent. Respondents will be asked for written consent to participate in the IBBA with an option of oral witnessed consent if they prefer. The purpose of the IBBA and the IBBA procedures will be explained in simple and understandable terms, in the local language. The potential participants will be informed that all information and discussions will remain confidential, their participation is voluntary, they may refuse to answer any questions and that they may leave the IBBA at any time. They will also be informed that their non-participation will not affect medical treatment if they seek it. The prospective participant will be asked to explain the activities of the IBBA back to the interviewer and witness to confirm an understanding of the procedure. The potential respondent will be asked to give written consent for the behavioral questionnaire and the biologic samples separately. If the prospective participant does not wish to give written consent, he/she may also give oral witnessed consent to participate in the IBBA. In the case of oral consent, once the members receiving the oral consent is convinced that the participant understands what has been agreed upon, the interviewer and the witness will sign on the consent form that declares:

"I have read and explained this informed consent form to the IBBA participant in (name of local language). The participant has explained the IBBA activities back to me and I am convinced that the participant understands the activities that will occur. The participant has not been coerced to participate and has given oral consent to participate in all aspects of this IBBA".

If the participant refuses to participate, the IBBA staff will respect the respondent's rights and thank them for their time.

4.2.3 Field data flow

Forms for each respondent will be kept in a folder. Each respondent will be given a unique respondent number. All forms for a given respondent will contain that number with the exception of the consent form. The questionnaire will contain information on location, time and date of interview, the name of the consent staff member, interviewer, doctor, supervisor and data entry clerk(s). The folder will contain:

- The consent form (signed and witnessed); and
- The completed questionnaire.

The supervisor will sign the cover of the folder after checking forms for accuracy and completeness. Immediately after checking the forms the consent form and the completed questionnaire will be separated. The folders will be taken to a secure location each night.

4.2.4 Field collection, Transport and Storage of Biological Specimens

Approximately 10 milliliters of venous blood will be collected in red top vacutainer tubes and labeled with the participant's unique number and date of collection. This will be placed in a cold box that will be transported to the district laboratory, at the end of each IBBA session each day. At the district laboratory, the specimen will be centrifuged, the serum aliquoted into four tubes and labeled with the IBBA respondent number and date of collection. After performing the syphilis tests, the serum will be retained for confirmation and quality control. All samples will be frozen for transport to the State Laboratory.

First catch urine samples (20ml) will be transported to the District Laboratory where they will be aliquotted into three 1ml tubes, and then frozen for transportation to the State Laboratory.

4.3 Laboratory Procedures

Blood, swabs and urine specimens will be picked up by the laboratory technicians for laboratory tests.

- HIV: Screening for HIV will be done using enzyme-linked immunosorbent assay (ELISA). A positive HIV screening test will be confirmed with a second ELISA and then undergo the BED-CEIA test (see below).
- Syphilis serologic testing performed on sera using a quantitative rapid plasma regain (RPR) screening test with a qualitative Treponema Pallidum Hemagglutination Assay (TPHA) confirmation test.
- Polymerase chain reaction (PCR) for *N. gonorrhoeae*, *C. trachomatis*. First catch of 20 ml urine will be stored in a cool box until they are transported for processing to

laboratories with capabilities to perform PCR tests.

- Multiplex Swab on reported and clinically identified genital or anal ulcers. Dacron swab stored dry at -70°C. Subject batched specimens to multiplex testing for *T pallidum*, *H ducreyi* and Herpes simplex Type 2.
- HSV-2 serology.
- HIV incidence testing: The newly developed BED-CEIA (HIV-1 subtypes B, E, and D, IgG-Capture Enzyme ImmunoAssay) that has also been validated with the Indian sub-type C assay will be used for measuring incidence of HIV.

4.3.1 Laboratory Sample Allocation and Management

At the district laboratory, the specimen will be centrifuged and divided into four aliquots of serum. One of the aliquots of serum will be used for syphilis testing locally, and the remaining aliquots stored frozen in preparation for transport to the state level laboratory.

The state laboratory will carry out the activities outlined and act as a staging station for frozen samples destined for the central laboratory.

The central laboratory (NARI in Pune) will receive and store all samples from the state laboratories, and carry out HIV incidence testing. All quality assurance activities will be managed from the central laboratory.

Long term storage of specimens: A protocol will be developed by ICMR and NARI on long-term storage of specimens so that specimens could be used for additional testing at a later time.

4.3.2 External Quality Assurance

The standard operating procedures and basic minimum standards will be agreed with NARI, who will draw up an implementing laboratory supervision and quality assurance schedule. Ten per cent (10%) of all samples will be re-tested in a different laboratory according to an agreed QA panel construction.

4.4 Data analysis

The questionnaires for the IBBA will be checked daily for completeness and accuracy by the field team supervisors and transported daily to a central location. At this center, the questionnaires will be stored in a secure place. Data on the questionnaires will be entered into EPI-INFO (or other appropriate data entry program) on a daily basis. Cluster information (needed for analysis) will also be entered into an appropriate database on a daily basis. All biological specimens will also be labeled with the corresponding unique identification number. Results of the laboratory tests will be entered into the database as and when the test results are available. Checks will be built into the data entry software to avoid data entry errors. Double data entry will be done to maximize accuracy. Analysis of

the IBBA data will be done in STATA for the TLS samples and with RDSAT for the RDS samples.

